5.5.5 Blinding

5.5.5.1 Blinding of Investigational Product

The active elagolix dose will be identical in appearance to its matched placebo; each active E2/NETA dose will be identical in appearance to its matched placebo. The study site personnel and subject will remain blinded to each subject's treatment during the blinded portion of the study (starting at the Treatment Month 3 visit and will continue until the end of the Treatment Period Month 24).

The IRT will provide access to blinded subject treatment information during the blinded portion of the study. AbbVie must be notified before the blind is broken, unless identification of the study drug is required for medical emergency, i.e., situation in which the knowledge of the specific blinded treatment will affect the immediate management of the subject/patient's conditions (AbbVie must then be notified within 24 hours after the blind being broken). The date and reason that the blind was broken must be recorded in the source documents and eCRF, as applicable.

5.5.6 Treatment Compliance

The Investigator or his/her designated and qualified representatives will administer/dispense study drug only to subjects enrolled in the study in accordance with the protocol. The study drug must not be used for reasons other than that described in the protocol.

Subjects will be instructed to return all study drug kits (even if empty, unused or damaged) to the study site personnel at on-site study visits throughout the Treatment Period, or Premature Discontinuation visit (if applicable). The study site personnel will assess dosing compliance at on-site visits.

Subjects should be advised of the importance of treatment compliance. Study drug should be taken consistently at approximately the same time in the morning for Day 1 – Treatment Month 3 and the same time in the morning and evening each day for Treatment Months 4 – 24.

5.5.7 Drug Accountability

The study Investigator or designee will verify via direct recording in IRT and/or by signature and date that study drug supplies are received intact and in the correct amounts indicated on the shipping document Clinical Site Shipment Request (CSSR) or similar shipping document. The shipment receipt must be acknowledged in IRT in order to become available for dispensation to subjects. The IRT must also be contacted when any subject completes or discontinues study drug treatment.

The IRT will maintain a current and accurate inventory of all clinical drug supplies, accountability, reconciliation, returns and destruction for each site. The IRT may also include the lot number, kit number, CSSR number, the number of pills/capsules dispensed and the date study drug was dispensed/returned for each subject. In addition to using IRT inventory, an accurate inventory of study drug may also be kept by the site.

An overall accountability of the study drug will be performed and verified by the site monitor via IRT throughout the study and at the study site closeout visit. Throughout the study and upon completion or termination of the study, all original containers will be returned to AbbVie according to instructions from AbbVie.

The study Investigator or his/her designated representative agrees not to supply study medication to any persons not enrolled in the study or not named as a sub-investigator.

Study drug will be dispensed at the study visits summarized in [Appendix C](#), Study Activities. Returned study drug should not be re-dispensed to the subject.

5.6 Discussion and Justification of Study Design

5.6.1 Discussion of Study Design and Choice of Control Groups

This is a Phase 3 study to investigate the long term safety and efficacy of elagolix in management of endometriosis with -associated moderate to severe pain in addition to providing efficacy data on dose adjustment of elagolix in women who are incomplete responders to elagolix 150 mg QD. This 24 month study will determine the impact of 24 months of elagolix 150 mg QD on bone mineral density as well as the long term impact of 200 mg BID and E2/NETA on bone mineral density (as measured by DXA). Additionally the study will evaluate women at risk for greater decreases in DXA based on modifiable risk factors.

5.6.2 Appropriateness of Measurements

The co-primary efficacy endpoints for this trial will be based upon the mutually-exclusive scales for daily assessment of DYS and NMPP measured by the 4-point Endometriosis Daily Pain Impact Diary. Use of protocol allowed rescue analgesic medication for endometriosis-associated pain will be included in the responder definition of the primary endpoints. Additional secondary efficacy measures of DYS and NMPP, dyspareunia, and the PGIC are widely used in endometriosis as assessment tools. In addition to assessment of pain reduction, the effects of treatment can be assessed using evidence of impact on subjects' functioning and overall well-being as well as subjects' utilization of health

resources and loss of time from work. Thus, PRO endpoints will also be utilized in the study.

The safety assessments used in this study are standard, widely used and generally recognized as reliable, accurate and relevant within the context of this study design.

For measurement of endometrial health, TVU has been selected as a reliable and established clinical assessment tool. TVU will also be utilized for evaluation of subjects for evidence of exclusionary gynecologic findings. Endometrial biopsy will provide a direct measure of any effect of elagolix on the endometrium.

DXA is a standard accepted measure of bone mineral density, and will be utilized to assess the effect of elagolix plus E2/NETA. Given the known relationship between estradiol levels and bone loss, serum E2 measurements will also be utilized to assess potential bone effects of elagolix plus E2/NETA.

5.6.3 Suitability of Subject Population

Premenopausal women 18 to 49 years of age with moderate to severe endometriosis-associated pain were selected for this study because this is the demographic that suffers from endometriosis with associated pain, including dyspareunia. No studies in males or females outside of their reproductive years are necessary for this indication.

5.6.4 Selection of Doses in the Study

Elagolix has a dose-dependent effect on BMD loss that is mediated through suppression of estradiol levels. Preliminary efficacy data from the completed Phase 3 clinical development program supports the ability of elagolix to reduce endometriosis-associated pain at both the 150 mg QD and 200 mg BID dose levels in a dose-dependent fashion (higher responder rate for 200 mg BID than for 150 mg QD). Also consistent with E2 suppression and findings from previous elagolix studies, there was a dose dependent effect on BMD, such that longer duration of treatment with the higher elagolix dose (200 mg BID) would likely require concomitant use of hormonal add back therapy to

mitigate BMD decrease. Furthermore, data from the Phase 2b study of elagolix in subjects with heavy menstrual bleeding due to uterine fibroids demonstrated the effect of E2/NETA on mitigating the BMD decrease associated with elagolix 300 mg BID. E2/NETA is approved for the prevention of osteoporosis in postmenopausal (estrogen-deficient) women.

As such, the elagolix 200 mg BID dose, in combination with E2/NETA add-back therapy was selected for this Phase 3 study, which will evaluate the safety and efficacy of this regimen in premenopausal women with moderate to severe endometriosis-associated pain. The objective is to generate data that would support a longer duration of use of this regimen for the proposed indication of management of endometriosis with associated pain, similar to the ongoing Phase 3 registration program.

6.0 Complaints

A Complaint is any written, electronic, or oral communication that alleges deficiencies related to the physical characteristics, identity, quality, purity, potency, durability, reliability, safety, effectiveness, or performance of a product/device after it is released for distribution.

Complaints associated with any component of this investigational product must be reported to the Sponsor (Section 6.2.2). For adverse events, please refer to Sections 6.1 through 6.1.5. For product complaints, please refer to Section 6.2.

6.1 Medical Complaints

The Investigator will monitor each subject for clinical and laboratory evidence of adverse events on a routine basis throughout the study. The Investigator will assess and record any adverse event in detail including the date of onset, event diagnosis (if known) or sign/symptom, severity, time course (end date, ongoing, intermittent), relationship of the adverse event to study drug, and any action(s) taken. For serious adverse events considered as having "no reasonable possibility" of being associated with study drug, the Investigator will provide an 'Other' cause of the event. For adverse events to be

considered intermittent, the events must be of similar nature and severity. Adverse events, whether in response to a query, observed by site personnel, or reported spontaneously by the subject will be recorded. All adverse events should be followed to a satisfactory conclusion.

6.1.1 Definitions

6.1.1.1 Adverse Event

An adverse event (AE) is defined as any untoward medical occurrence in a patient or clinical investigation subject administered a pharmaceutical product and which does not necessarily have a causal relationship with this treatment. An adverse event can therefore be any unfavorable and unintended sign (including an abnormal laboratory finding), symptom, or disease temporally associated with the use of a medicinal (investigational) product, whether or not the event is considered causally related to the use of the product.

Such an event can result from use of the drug as stipulated in the protocol or labeling, as well as from accidental or intentional overdose, drug abuse, or drug withdrawal. Any worsening of a pre-existing condition or illness is considered an adverse event. Any worsening of a subject's endometriosis-associated pain during the course of the study will not be captured as an adverse event unless it meets the criteria for a serious adverse event (Section 6.1.1.2), at which point, it will be reported as such. Worsening in severity of a reported adverse event should be reported as a new adverse event. Laboratory abnormalities, changes in BMD (during the Treatment Period) and changes in vital signs are considered to be adverse events only if they result in discontinuation from the study, necessitate therapeutic medical intervention, and/or if the Investigator considers them to be adverse events.

An elective surgery/procedure scheduled to occur during a study will not be considered an adverse event if the surgery/procedure is being performed for a pre-existing condition and the surgery/procedure has been pre-planned prior to study entry. However, if the pre-existing condition deteriorates unexpectedly during the study (e.g., surgery performed

earlier than planned), then the deterioration of the condition for which the elective surgery/procedure is being done will be considered an adverse event.

6.1.1.2 Serious Adverse Events

If an adverse event meets any of the following criteria, it is to be reported to AbbVie as a serious adverse event (SAE) within 24 hours of the site being made aware of the serious adverse event.

Death of Subject	An event that results in the death of a subject.
Life-Threatening	An event that, in the opinion of the Investigator, would have resulted in immediate fatality if medical intervention had not been taken. This does not include an event that would have been fatal if it had occurred in a more severe form.
Hospitalization or Prolongation of Hospitalization	An event that results in an admission to the hospital for any length of time or prolongs the subject's hospital stay. This does not include an emergency room visit or admission to an outpatient facility.
Congenital Anomaly	An anomaly detected at or after birth, or any anomaly that results in fetal loss.
Persistent or Significant Disability/Incapacity	An event that results in a condition that substantially interferes with the activities of daily living of a study subject. Disability is not intended to include experiences of relatively minor medical significance such as headache, nausea, vomiting, diarrhea, influenza, and accidental trauma (e.g., sprained ankle).

Important Medical Event Requiring Medical or Surgical Intervention to Prevent Serious Outcome

An important medical event that may not be immediately life-threatening or result in death or hospitalization, but based on medical judgment may jeopardize the subject and may require medical or surgical intervention to prevent any of the outcomes listed above (i.e., death of subject, life-threatening, hospitalization, prolongation of hospitalization, congenital anomaly, or persistent or significant disability/incapacity). Additionally, any elective or spontaneous abortion or stillbirth is considered an important medical event. Examples of such events include allergic bronchospasm requiring intensive treatment in an emergency room or at home, blood dyscrasias or convulsions that do not result in inpatient hospitalization, or the development of drug dependency or drug abuse.

For serious adverse events with the outcome of death, the date and cause of death will be recorded on the appropriate case report form.

6.1.1.3 Adverse Events of Special Interest

Some adverse events, such as SAEs and adverse events of special interest (AESI), may require additional information to be collected, including family history. AESIs include, but are not limited to rash/hypersensitivity, fracture, neuro-psychiatric (depression, mood swings, etc.) and vasomotor symptoms (e.g., hot flush, night sweats).

6.1.2 Adverse Event Severity

The Investigator will use the following definitions to rate the severity of each adverse event:

- | | |
|-----------------|---|
| Mild | The adverse event is transient and easily tolerated by the subject. |
| Moderate | The adverse event causes the subject discomfort and interrupts the subject's usual activities. |
| Severe | The adverse event causes considerable interference with the subject's usual activities and may be incapacitating or life-threatening. |

6.1.3 Relationship to Study Drug

The Investigator will use the following definitions to assess the relationship of the adverse event to the use of study drug:

Reasonable Possibility	After consideration of factors including timing of the event, biologic plausibility, clinical judgment, and potential alternative causes, there is sufficient evidence (information) to suggest a causal relationship.
No Reasonable Possibility	After consideration of factors including timing of the event, biologic plausibility, clinical judgment, and potential alternative causes, there is insufficient evidence (information) to suggest a causal relationship.

For causality assessments, events assessed as having a reasonable possibility of being related to the study drug will be considered "associated." Events assessed as having no reasonable possibility of being related to study drug will be considered "not associated." In addition, when the Investigator has not reported causality or deemed it not assessable, AbbVie will consider the event associated.

[figure not shown]
If an Investigator's opinion of "no reasonable possibility of being related to study drug" is given, another cause of event must be provided by the Investigator for serious adverse events.

6.1.4 Adverse Event Collection Period

All adverse events reported from the time of study drug administration until 30 days following discontinuation of study drug have elapsed will be collected, whether solicited or spontaneously reported by the subject. All nonserious adverse events of bone fracture, clinically significant BMD loss, or newly diagnosed medically-related bone condition will be collected during the Follow-Up Period, until the subject discontinues from study participation. In addition, serious adverse events and protocol-related nonserious adverse events will be collected from the time the subject signed the study-specific informed consent.

Adverse event information will be collected as shown in Figure 2.

Figure 2. Adverse Event Collection

6.1.6 Pregnancy

Pregnancy in a study subject must be reported to AbbVie within 1 working day of the site becoming aware of the pregnancy. Subjects who become pregnant during the Treatment or Follow-Up Periods of the study must be discontinued (Section 5.4 and Section 5.4.1). A positive urine pregnancy test result must be confirmed with a serum pregnancy test. While waiting for the results of the serum pregnancy test, study drug should be temporarily discontinued pending results of the serum pregnancy test. If a serum pregnancy test result is positive at any time during the Treatment Period of the study, the site will immediately inform the subject to discontinue study drug. Information regarding a pregnancy occurrence in a study subject and the outcome of the pregnancy will be collected for any study subject with a positive serum pregnancy test from the signing of the informed consent (i.e., washout [if applicable] or screening) through completion of the Follow-Up Month 1 visit. The site will report a positive pregnancy test to the Sponsor, will follow the course of the subject's pregnancy, and report to the Sponsor on the health of the subject and fetus at each trimester, the newborn at the first post-delivery pediatrician visit and the infant 6 – 12 months post-delivery.

If the subject becomes pregnant during the study, no additional study procedures, including protocol required DXA scans, will be conducted. However, an ultrasound examination will be performed as early as possible during the first trimester of pregnancy to assess the gestational age and document an intrauterine pregnancy. The following information on the outcome of a pregnancy that occurs after signing of the informed consent, regardless of when the subject became pregnant (i.e., either during the Washout, Screening, Treatment or through Follow-Up Month 1) should be collected: fetal outcome (e.g., spontaneous or elective abortion, live infant or still birth), date and mode of delivery, birth weight, birth length, gender, congenital anomaly and medically significant complications during pregnancy or labor or delivery. For live infant births, information on the health of the infant will be collected from the first post-delivery pediatrician visit and at 6 to 12 months after delivery.

Pregnancy in a study subject is not considered an adverse event. However, the medical outcome for mother or infant meeting any serious criteria including an elective or spontaneous abortion, stillbirth or congenital anomaly is considered a serious adverse event and must be reported to AbbVie within 24 hours of the site becoming aware of the event.

6.2 Product Complaint

6.2.1 Definition

A Product Complaint is any Complaint (see Section 6.0 for the definition) related to the biologic or drug component of the product.

For a product this may include, but is not limited to, damaged/broken product or packaging, product appearance whose color/markings do not match the labeling, labeling discrepancies/inadequacies in the labeling/instructions (example: printing illegible), missing components/product, or packaging issues.

Any information available to help in the determination of causality by the product to the events outlined directly above should be captured.

6.2.2 Reporting

Product Complaints concerning the investigational product must be reported to the Sponsor within 24 hours of the study site's knowledge of the event via the Product Complaint form. Product Complaints occurring during the study will be followed-up to a satisfactory conclusion. All follow-up information is to be reported to the Sponsor (or an authorized representative) and documented in source as required by the Sponsor. Product Complaints associated with adverse events will be reported in the study summary. All other complaints will be monitored on an ongoing basis.

Product Complaints may require return of the product with the alleged complaint condition (investigational product). In instances where a return is requested, every effort should be made by the Investigator to return the product within 30 days. If returns cannot

be accommodated within 30 days, the site will need to provide justification and an estimated date of return.

The description of the complaint is important for AbbVie in order to enable AbbVie to investigate and determine if any corrective actions are required.

7.0 Protocol Deviations

AbbVie does not allow intentional/prospective deviations from the protocol unless when necessary to eliminate an immediate hazard to study subjects. The Principal Investigator is responsible for complying with all protocol requirements, and applicable global and local laws regarding protocol deviations. If a protocol deviation occurs (or is identified) after a subject has been enrolled, the principal investigator is responsible for notifying Independent Ethics Committee (IEC)/Independent Review Board (IRB) regulatory authorities (as applicable), and their assigned Clinical Monitor or the following AbbVie Clinical Study Team Members:

Primary Contact:

Alternate Contact:

Such contact must be made as soon as possible to permit a review by AbbVie to determine the impact of the deviation on the subject and/or the study.

8.0 Statistical Methods and Determination of Sample Size

8.1 Statistical and Analysis Plans

8.1.1 General Considerations

The SAS system will be used to perform the statistical analyses. All statistical tests will be two-sided and a significance level of 0.05 will be used unless otherwise specified. A test will be deemed statistically significant if the *P* value rounded to three decimal places is less than or equal to 0.05 unless otherwise specified. The primary efficacy comparisons will be at Treatment Month 6 between the elagolix 200 mg BID plus E2/NETA treatment group (Group C) and elagolix 150 mg QD group (treatment Group B) in patients who are incomplete responders to elagolix 150 mg QD treatment at Month 3.

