8.3 Determination of Sample Size

This study plans to enroll approximately 890 subjects to ensure a sufficient number of subjects receive elagolix 150 mg QD for 24 months.

Assuming the efficacy responder rate for the Daily Diary endometriosis-associated pain score via NRS is 50% during the open label elagolix 150 mg QD group at Month 3, 50% of subjects who complete Month 3 of the open-label period and are incomplete responders to 150 mg QD will be randomized in equal ratio to 150 QD and 200 BID plus E2/NETA.

Among those, assuming Month 6 DYS and NMPP responder rates of 20% for subjects who are randomized to elagolix 150 mg QD group (Group B) and 50% for subjects who are randomized elagolix 200 mg BID plus E2/NETA treatment group (Group C), this sample size provides greater than 90% power to detect a difference in response rate based on a 2-sided test at the significance level of $\alpha = 0.05$. The above sample size was calculated using nQuery advisor 7.0.

Assuming 80% of incomplete responders to 150 mg QD who are randomized to 150 QD at Month 3 are switched to elagolix 200 mg BID plus E2/NETA at Month 6 and a 25% completion rate, the current sample size will provide at least 120 subjects who receive elagolix 150 mg QD treatment group for 24 months (Group A and E).

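### Section 8.1.1 tests a rounded P value against 0.05, which puts the nominal cut-off at 0.0505 instead of the stated 0.05 (minor, wrong as written)

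*Combined protocol and SAP*

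**What the plan says.** Protocol section 8.1.1 (General Considerations) has two consecutive sentences on significance. The first fixes the level: "All statistical tests will be two-sided and a significance level of 0.05 will be used unless otherwise specified". The second defines how a result is judged: a test counts as significant if the P "value rounded to three decimal places is less than or equal to 0.05".

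Both sentences allow exceptions, but none is given for the primary analysis. Section 8.1.4.2.1 specifies a logistic regression of responder status at Month 6 on treatment and baseline pain score, comparing Group C with Group B for DYS and for NMPP. It also plans a repeat based on percent change. It sets no separate significance rule for either, and neither does section 8.1.4.1.

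Section 8.3 states the power on the unrounded level: "greater than 90% power to detect a difference in response rate based on a 2-sided test at the significance level of" 0.05.

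**The concern.** The level and the decision rule are different rules. A P value of 0.0504 is not significant at level 0.05, yet it becomes 0.050 when rounded and so passes. The plan therefore gives two answers for the same result, and the operative one is the more lenient.

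The shift goes one way only. A P value at or below 0.05 never rounds above 0.050, so rounding cannot turn a significant result into a non-significant one, and nothing offsets the leniency.

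What is at stake is narrow. Unless otherwise specified, the protocol plans no tests for the secondary efficacy endpoints (8.1.4.3) or safety (8.1.5.1), and no between-group comparisons of BMD (8.1.5.4). That leaves the two co-primary tests and their percent-change repeat.

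**Working it through.** **Inputs from the documents.** Two-sided level 0.05 and the three-decimal rule (8.1.1). From 8.3: about 890 enrolled, 50% incomplete responders at Month 3, 1:1 randomization, responder rates of 20% (Group B) and 50% (Group C), stated power above 90%.

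**Assumption.** The documents give no loss rate before Month 3, so 0% to 50% is used as a range.

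**1. The plan's own power figure at the unrounded level.**
- Per arm with no loss: 890 × 0.5 / 2 = 222.5, taken as 222.
- Per arm with 50% loss: 890 × 0.5 × 0.5 / 2 = 111.25, taken as 111.
- Normal approximation: power = Φ{[0.30 − z·√(2·0.35·0.65/n)] / √[(0.2·0.8 + 0.5·0.5)/n]}, with z = 1.9600.
- n = 222: Φ[(0.30 − 0.0887)/0.0430] = Φ(4.92), above 0.9999.
- n = 111: Φ[(0.30 − 0.1255)/0.0608] = Φ(2.87) = 0.9980.

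The stated power above 90% reproduces for each co-primary test over the whole assumed range.

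**2. The cut-off that the rounding rule implies.**

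| Unrounded P | Rounded | P ≤ 0.05? | Significant under 8.1.1 rule? |
|---|---|---|---|
| 0.0499 | 0.050 | yes | yes |
| 0.0500 | 0.050 | yes | yes |
| 0.0501 | 0.050 | no | yes |
| 0.05049 | 0.050 | no | yes |
| 0.0505 | 0.051 (half up) | no | no |
| 0.05051 | 0.051 | no | no |

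The two rules disagree only for P strictly above 0.05 and below 0.0505. Exactly 0.0505 would also pass under half-to-even rounding; the protocol does not name the convention.

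**3. Size of the shift.**
- Excess: 0.0505 − 0.0500 = 0.0005; relative: 0.0005 / 0.05 = 1%.
- Critical |z|: 1.9600 at 0.05, 1.9557 at 0.0505.
- If P were exactly uniform under the null, 0.0005 is 1 null result in 2,000.

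**4. Effect on power and sample size.** With z = 1.9557, power at 111 per arm is still 0.9980, and at 222 it still exceeds 0.9999. For 90% power the formula needs 52 per arm at 0.05 and 51 at 0.0505. Under the planning rates, the chance that a test lands between the two cut-offs is about 1 in 100 million at 222 per arm and about 3 in 100,000 at 111.

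**5. Nominal cut-off against actual size.** The size of an unadjusted logistic comparison was enumerated exactly at 222 per arm (no loss before Month 3), for a common responder rate in both groups.

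| Common rate | Test | Unrounded rule | Rounded rule |
|---|---|---|---|
| 20% | Wald | 0.0488 | 0.0498 |
| 20% | Likelihood ratio | 0.0509 | 0.0517 |
| 30% | Wald | 0.0496 | 0.0496 |
| 50% | Either | 0.0516 | 0.0516 |

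Actual size runs from about 0.049 to 0.052 under either rule. The planned model adds baseline pain score, which smooths the discreteness, so these figures are illustrative. They show that the asymptotic approximation can matter more than the rounding.

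**The case against.** The best case against raising this is that the rule is disclosed in advance, leaves no discretion after the data are seen, and has almost no chance of affecting this trial. It can also be overridden: both sentences allow exceptions, section 8.1.4 defers analysis details to the SAP, and the text available for review contains no separate SAP against which to check for another rule. Most of this stands. It limits the importance of the point, but pre-specifying the rule does not make its nominal level 0.05, and the protocol still states two rules that conflict.

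Three stronger readings are tempting and are not supported.

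- **The true type I error is 0.0505.** This needs a P value that is exactly uniform under the null. Here the outcome is binary and the test asymptotic. In the illustrative enumeration, the Wald size at a 20% common rate is below 0.05 under both rules, and at 50% it is above 0.05 under both. Only the nominal cut-off is shown to be wrong.
- **The sample size or power in section 8.3 is undermined.** It is not; the power is the same to four decimals at 111 per arm under either cut-off.
- **The excess adds up over the two co-primary tests.** The protocol calls the endpoints co-primary but states no explicit success rule. If both must succeed, which is the usual meaning, the nominal joint error is at most 0.0505.

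**Conclusion.** The decision rule in section 8.1.1 is wrong as written, and the matter is minor. It replaces the stated nominal cut-off of 0.05 with 0.0505 for each co-primary test, an anti-conservative excess of 0.0005. A conclusion can change only if an unrounded P lies strictly above 0.05 and below 0.0505, and then always towards success.

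This rests on ordinary half-up rounding and on there being no overriding rule elsewhere; none appears in sections 8.1.4.1 to 8.1.4.3 or 8.3. It makes no claim about the finite-sample error rate of the logistic regression test.

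**What to change.** Replace the second sentence of the rule in section 8.1.1, or override it in the SAP, so that a test is significant when the unrounded two-sided P value is at most 0.05. Say that rounding to three decimals applies only to the display of P values in tables and text.

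The cost is one sentence. Sample size, data collection and trial conduct do not change. Section 8.1.4.2.1 already requires a final SAP before the blind is broken to carry the ROC thresholds, so the correction can go into that document. The change makes the nominal cut-off agree with the stated level; it does not make the asymptotic test exact.
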